#### 7. Treatment

#### 7.1. Treatment Administered

The doses to be administered are presented in Section 5.1.1.

The IP will be administered either via a SC injection or as a slow IV bolus (over at least 1 minute). A maximum of 2 injections may be necessary to achieve higher planned dose levels.

- For SC cohorts, LY3493269 and placebo will be administered at a maximum volume of 2 mL per injection.
- Participants in the IV Cohort will be dosed one at a time, at least 20 minutes apart.

For IV doses, investigative sites must have resuscitation equipment, emergency drugs, and appropriately trained staff available during IV dosing and for at least 6 hours after participants have completed their IV dose.

Table GZHA.3 shows the treatment regimens.

Table GZHA.3. Treatments Administered

Treatment Name	LY3493269	Placebo			
Dosage Formulation	Lyophilized powder a	0.9% sodium chloride injection			
Unit dose strength	5mg/vial LY3493269	N.A.			
Route of Administration	SC injection or IV dose	SC injection			
Dosing instructions	Single injection or IV dose (at the assigned dose level)	Single injection (volume matched with active drug			

Abbreviations: IV = intravenous, SC = subcutaneous.

The investigator or designee is responsible for:

- explaining the correct use of the IPs to the participant and site personnel
- verifying that instructions are followed properly
- maintaining accurate records of IP dispensing and collection
- and returning all unused medication to Lilly or its designee at the end of the study

**Note:** In some cases, sites may destroy the material if, during the investigative site selection, the evaluator has verified and documented that the site has appropriate facilities and written procedures to dispose of clinical materials.

a Reconstituted with sterile water for injection.

## 7.1.1. Injection Sites

All injections will be administered into the SC tissue of the abdominal wall, in the right or left upper or lower quadrant. Where more than 1 injection is required to deliver a full dose, it is recommended that the injections are administered in opposite quadrants, such as upper right and lower left or upper left and lower right. Whenever possible, IP administration should be carried out by the same personnel and at approximately the same time of day in all cohorts. The actual time of dosing and the site(s) of injection(s) will be recorded in the participant's case report form (CRF).

## 7.1.2. Packaging and Labeling

The drug product LY3493269 is supplied for clinical trial use as 5 mg lyophilized powder in a glass vial. Further dilution may be needed for IV administration. Detailed instructions for the preparation of LY3493269 will be included in the Pharmacy Instructions provided by the sponsor.

Placebo will be provided as sterile saline (0.9% NaCl) in a 50 mL vial. Placebo doses should be held in the pharmacy for an equivalent amount of time as is required to prepare doses of LY3493269.

Both materials will be labeled according to the country's regulatory requirements.

#### 7.2. Method of Treatment Assignment

Randomization tables for allocation of LY3493269 or placebo to participants will be prepared by the statistician for the study and provided to the site pharmacists involved in dose preparation. The allocation and dispensing of the IPs will be fully documented and verified by a second person. Detailed records of the amounts of the IP received, dispensed, and remaining at the end of the study will be maintained by the site pharmacist.

## 7.2.1. Selection and Timing of Doses

The doses will be administered at approximately the same times on each day. The actual time of all dose administrations will be recorded in the participant's CRF.

## 7.3. Blinding

This is an investigator- and participant-blind study for SC Cohorts 1 through 6. To preserve the blinding of the study for LY3493269 and placebo, all study site personnel, except pharmacy staff who prepare and dispense study medication, will be blinded to treatment allocation.

Blinding will be maintained throughout the conduct of the study as described in the Blinding/Unblinding Plan.

Emergency codes will be available to the investigator. A code, which reveals the treatment for a specific study participant, may be opened during the study only if the participant's well-being requires knowledge of the participant's treatment assignment.

If the study treatment assignment for participants in the SC cohorts is unblinded, the participant must be discontinued from the study, unless the investigator obtains specific approval from a Lilly clinical pharmacologist or clinical research physician (CRP) for the study participant to continue in the study. During the study, emergency unblinding should occur only by accessing the study participant's emergency code.

In case of an emergency, the investigator has the sole responsibility for determining if unblinding of a participant's treatment assignment is warranted for medical management of the event. The participant's safety must always be the first consideration in making such a determination. If the investigator decides that unblinding is warranted, it is the responsibility of the investigator to promptly document the decision and rationale and notify Lilly as soon as possible.

Upon completion of the study, all codes must be returned to Lilly or its designee.

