## 5.1.3. Follow-Up Visits (Days 29 and 43)

On Days 29 and 43, two follow-up visits will occur where participants will undergo study assessments specified in the Schedule of Activities (Section 2).

Participants who received IP and who discontinue early will be encouraged to return for follow-up visit(s) for safety monitoring, including but not limited to 28 days after IP administration. All enrolled participants who discontinue without receiving IP will observe an early termination visit with procedures performed as shown in the Schedule of Activities (Section 2).

Participants will be discharged after the investigator has completed review of all final safety assessments from the last follow-up visit.

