#### 8. Discontinuation Criteria

Participants discontinuing from the study prematurely for any reason must complete adverse event and follow-up procedures per Section 2 of this protocol.

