# 8.1. Discontinuation from Study Treatment

Participants will only receive 1 dose of IP and hence cannot be discontinued from the study treatment.

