# 8.2. Discontinuation from the Study

Participants will be discontinued in the following circumstances:

- Enrollment in any other clinical study involving an IP or enrollment in any other type of medical research judged not to be scientifically or medically compatible with this study
- Participation in the study needs to be stopped for medical, safety, regulatory, or other reasons consistent with applicable laws, regulations, and good clinical practice (GCP)
- Investigator Decision
  - o the investigator decides that the participant should be discontinued from the study
  - o if the participant, for any reason, requires treatment with another therapeutic agent that has been demonstrated to be effective for treatment of the study indication, discontinuation from the study occurs prior to introduction of the new agent
- Participant Decision
  - o the participant, or legal representative, requests to be withdrawn from the study.

The replacement strategy for discontinued participants is described in Section 10.1. If deemed appropriate by the investigator, early discontinuation procedures will be performed as shown in the Schedule of Activities (Section 2).

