# 10. Statistical Considerations and Data Analysis

# 10.1. Sample Size Determination

The sample size is customary for Phase 1 studies evaluating safety and PK and is not powered on the basis of statistical hypothesis testing.

Participants who are randomized but not administered treatment prior to discontinuation may be replaced to ensure that approximately 8 participants may complete each SC Cohort, and 6 to complete the IV cohort.

Participants who discontinue early may be replaced after consultation with the investigator and sponsor. The replacement participant will be assigned to the same treatment as the discontinued participant.

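### Opening a participant's code in the SC cohorts makes discontinuation from the study the default; after a single dose this stops no treatment, can cut PK, ADA and safety observation to one visit, and may unmask a replacement

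*Protocol*

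**What the plan says.** Protocol 7.3 restricts code-breaking: a code "may be opened during the study only if the participant's well-being requires knowledge of the participant's treatment assignment". For the SC cohorts it then sets the consequence: "If the study treatment assignment for participants in the SC cohorts is unblinded, the participant must be discontinued from the study". The same sentence carries an exception, "unless the investigator obtains specific approval from a Lilly clinical pharmacologist or clinical research physician (CRP". Section 8.1 notes that "Participants will only receive 1 dose of IP and hence cannot be discontinued from the study treatment".

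The follow-up owed after discontinuation appears in three places:

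- Section 8: anyone leaving early, for whatever reason, "must complete adverse event and follow-up procedures per Section 2 of this protocol".
- Section 5.1.3: "Participants who received IP and who discontinue early will be encouraged to return". The next sentence is firmer for participants who were never dosed, who are to have an ET visit.
- Section 8.2: "If deemed appropriate by the investigator, early discontinuation procedures will be performed".

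The ET column of the SC schedule includes AEs, vital signs, ECG, safety laboratory tests, one PK sample and one immunogenicity sample. Section 9.2 requires serious, related or otherwise medically important AEs to be followed until they resolve, stabilise or are explained. SAP 9.1 lists a participant's data only as far as withdrawal.

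On replacement, Section 10.1 (repeated in SAP 7) makes it optional after consultation with the investigator and sponsor, and adds: "The replacement participant will be assigned to the same treatment as the discontinued participant". Section 7.3 refers to a separate Blinding/Unblinding Plan, which was not among the documents reviewed.

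**The concern.** Discontinuation after unblinding has an obvious purpose when dosing continues. Here the single dose has already been given, so the rule has nothing to act on except observation. It applies to participants whose condition was worrying enough to need the code, in a study whose primary endpoint is TEAEs and SAEs. Some decisions also depend on continued observation: one termination criterion in 7.4.2 turns on symptoms lasting more than a week.

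Two things are at stake. The first is completeness: later safety assessments, the PK profile that would relate exposure to the event, and the Day 15 to Day 43 ADA samples. The second is the blind. An investigator who has read a discontinued participant's code, and is consulted on the replacement, can infer the replacement's treatment before dosing, and then judges severity and relatedness in that person.

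**Working it through.** **1. The plan's own figures.** Six SC cohorts of 8 plus one IV cohort of 6 gives 6 × 8 + 6 = 54, the planned number of completers. With up to 70 enrolled, 70 − 54 = 16 places are spare, so replacement is feasible. The SC schedule has 12 PK samples (predose, 6, 12, 24, 48, 72, 96, 120 and 168 h, Days 15, 29 and 43) and 4 ADA samples (predose, Days 15, 29 and 43). Both counts agree with Appendix 5.

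**2. Sampling at risk.** Outstanding = scheduled − already taken. An ET visit gives back one PK and one ADA sample. For removal after 24 h: PK 12 − 4 = 8, ADA 4 − 1 = 3; net of ET, 7 and 2.

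| Last sample before removal | PK outstanding | ADA outstanding | Net loss with one ET visit (PK, ADA) |
|---|---|---|---|
| 24 h | 8 | 3 | 7, 2 |
| 72 h | 6 | 3 | 5, 2 |
| 168 h | 3 | 3 | 2, 2 |
| Day 15 | 2 | 2 | 1, 1 |

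An ET sample taken in the first days also says little about ADA formed later.

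**3. What the three wordings do to the same case (removal after 24 h).**

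- Section 8, read as still requiring the Day 29 and Day 43 visits: 48, 72, 96, 120 and 168 h and Day 15 are missed, so 6 PK and 1 ADA.
- A single ET visit: 7 PK and 2 ADA.
- Section 8.2, with the investigator judging no procedures appropriate and no return under 5.1.3: 8 PK and 3 ADA.

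**4. What that means for AUC (conditional).** Table GZHA.2 gives AUC/Cmax = 7670/31.2 = 246 h at the lowest dose and 386000/1580 = 244 h at the highest. Assume one-compartment kinetics, so AUC/Cmax = exp(k·tmax)/k, and tmax between 12 and 72 h. The half-life is then 6.7 to 4.4 days. The share of AUC still to come at time t is at least exp(−kt): 0.85 to 0.90 at 24 h and 0.62 to 0.73 at 72 h. Without later samples, the extrapolated part of AUC(0-∞) would far exceed the 20% at which SAP 9.3.1 flags the value.

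**5. Weight of one case.** One active participant is 1/6 = 16.7% of a dose level.

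**6. The replacement.** Before any code is opened, an SC participant's chance of being on active drug is 6/8 = 0.75. If a participant whose code was opened is replaced under the same-treatment rule, the investigator's probability for the replacement becomes 1 or 0. If the participant is retained instead, the odds for the other seven only shift, to 5/7 = 0.71 (opened code active) or 6/7 = 0.86 (opened code placebo).

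**7. Frequency.** The documents give no code-break rate. As an assumption only, 1% to 5% per participant over 48 SC participants gives a chance of at least one of 1 − 0.99^48 = 0.38 to 1 − 0.95^48 = 0.91.

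**The case against.** A reader might infer from 7.3 that an opened code always means removal and that follow-up is then lost. The documents do not support that. The sentence contains a sponsor-approval exception, and the investigator must notify the sponsor of any code-break promptly, so approval can be sought at the same time. Section 8 is mandatory in form, Section 9.2 follows the important AEs to their conclusion, and the ET visit keeps one PK and one ADA sample. The inpatient stay can also be extended for safety. What is mainly exposed is intermediate PK and ADA sampling, which serves secondary and exploratory objectives. The SAP also flags heavily extrapolated AUC values. All of this stands, and it limits the size of the point. It does not give the default a purpose or settle which of the three follow-up wordings governs.

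A reader might also infer that a replacement's allocation is always revealed. It is not: replacement is optional, and under 7.4.2 one related SAE on active drug stops dosing at that level, which removes the most serious route to a same-dose replacement. The Blinding/Unblinding Plan may hold a safeguard. Section 7.4.1 also presumes relatedness unless there is clear evidence otherwise, which leaves less room for bias in that judgement. The leak is therefore conditional, but nothing in the protocol or SAP text excludes it.

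Finally, it is tempting to say that participants whose codes are opened are more likely to be on active drug at high dose. That is plausible, but the documents offer nothing to show it.

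Part of the variation in wording may reflect that someone who withdraws cannot be compelled to return. That explains softer language for withdrawal of consent, but not for a discontinuation that the protocol itself imposes.

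**Conclusion.** The point holds in a limited form. For a dosed SC participant, the default after a code-break stops no treatment and can reduce scheduled observation, in the worst documented cases to one ET visit or none. After removal at 24 h the net loss is 7 of 12 PK and 2 of 4 ADA samples with an ET visit, or 8 and 3 without one. One active participant is 1 of 6 at the dose. AE follow-up is partly protected, so the primary endpoint is less exposed than PK and ADA. Unmasking of a replacement requires that the participant is replaced, that the investigator opened the code, and that the unseen Blinding/Unblinding Plan has no safeguard.

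The sample counts rest only on the schedule. The AUC shares rest on one-compartment kinetics and an assumed tmax, and the chance of any code-break on an assumed rate. It is also an assumption that discontinuation after unblinding counts as withdrawal for the SAP 9.1 listings, since the SAP does not say. Confidence is moderate. The change should be made because it is cheap and the conflict in wording matters even if no code is opened.

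**What to change.** - **Protocol 7.3:** make it the default that a dosed participant whose code is opened stays in the study for all scheduled safety, PK and ADA assessments through Day 43, unless consent is withdrawn. Record the date and reason for unblinding, and flag later AE assessments as unblinded.
- **Protocol 5.1.3, 8 and 8.2, and SAP 9.1:** reconcile these to one follow-up rule and one listing rule for dosed participants, so that data collected after a code-break are listed.
- **Protocol 10.1 (and SAP 7):** state that a dosed participant retained after unblinding is not replaced. This removes the leak at its source. Drawing replacements from an unlinked reserve list is not advised, because it could disturb the 6:2 allocation.
- **Blinding/Unblinding Plan:** confirm that it covers the remaining case, a participant who withdraws consent after the code is opened and is then replaced.

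The cost is wording in the protocol and SAP, with no visits beyond those already scheduled. The one small downside is that AE assessments after unblinding come from an unblinded assessor, which is why they need the flag.

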#### 7.4. Dose Modification for Subcutaneous Cohorts Only

In cohorts receiving SC doses, dose levels or increments, sampling schedule, and length of stay at the CRU may be adjusted in view of emerging safety, tolerability, or PK/PD data during the study.

If considered appropriate:

- Dose increments for SC doses may be reduced, a dose level may be repeated, or a lower/intermediate dose may be administered, but dose escalations will not exceed a halflog (3.3-fold) increase in dose.
- The timing of the sampling may be adjusted and additional samples may be collected, as described in Section 9.6.
- The duration of the CRU stay or the duration of safety follow-up may be increased (for example if the half-life of LY3493269 is longer than anticipated) but not decreased.

These changes must be appropriately documented and communicated by the sponsor to the investigator. Because these adjustments to timings or dose levels are allowable changes permitted by the protocol, they would not require a protocol amendment. However, any changes to the planned dose levels, together with the supporting data, will be reviewed by a SRP, composed of members independent of the study team and investigative site.

#### 7.4.1. Dose Decision/Escalation

By nature of being a dose escalation study, data will be evaluated on an ongoing basis until the maximum tolerated dose (MTD) is determined or when stopping criteria are met. The highest dose level that is tolerated will be designated as the MTD for single SC doses in healthy participants. Interim access to study data is scheduled to occur during the study to inform dose escalation decisions, as specified in Section 10.3.6.

Safety data will be the primary criteria for the dose escalation. In addition, if available at the time of dose escalation decision, PK and/or PD results may be used as supporting data for dose

escalation, but such data are not required. No dose decision can occur without prior discussion and agreement between the investigator and the Lilly clinical pharmacologist.

Prior to dose escalation, all planned participants in the current cohort should have been dosed prior to escalation to next cohort. The investigator and sponsor must review safety and tolerability data up to at least 7 days postdose from at least 6 participants receiving IP at the current dosing level, including but not limited to ECGs, clinical laboratory tests, vital signs, body weight, appetite VAS scores and AEs. After review of these data, an escalation to the next dose level will be jointly decided by the investigator and sponsor. The magnitude of dose escalation may be reduced following data review, but subsequent escalations cannot be increased by more than approximately 3.3 fold (a half-log increment); dose levels may be repeated if warranted following data review.

Safety data, in particular AEs, SAEs, and adverse laboratory abnormalities, will be independently assessed by the investigator, and will be considered related to the IP unless there is clear evidence that the event is not related.

# 7.4.2. Termination of Dosing/Dose Escalation

If any of the following scenarios occur, dosing at the current level and further dose escalation will be discontinued:

- 1) One or more participants on active drug experience an SAE considered to be related to LY3493269
- 2) One or more participants on active drug experience 2 clinically significant events defined as moderate to severe symptoms, clinical signs, and clinical laboratory findings that could cause harm to health. CSEs will be determined by the investigator or suitable designee and may include findings that do not fulfill the criteria for SAEs
- 3) Three or more participants at the same dose level experience any of the following deemed to be related to LY3493269 administration:
  - drug-related GI effects (for example emesis, diarrhea) causing severe distress (prevents daily activities or requires an emergency department visit or hospitalization); and/or
  - clinically significant cardiovascular AEs
  - a symptomatic hypoglycemic episode with BG values <2.7 mmol/L (48.6 mg/dL; corresponding to plasma glucose levels of <3.0 mmol/L [54 mg/dL])
- 4) Two or more participants on active drug develop persistent (>1 week) symptoms suggestive of acute pancreatitis. Refer to algorithm for the monitoring of asymptomatic hyperenzymemia in Appendix 6.

#### 7.4.2.1. Premedication for IV Administration

Premedication for the IV administration is not planned. However, if a reaction occurs after dosing the first 2 participants (Section 5.1), appropriate medication may be used in subsequent

participants in the cohort. If postdose reactions are observed in the first 2 participants, but review of the data suggests that dosing of subsequent participants may continue, administration of acetaminophen, 500 to 1000 mg, and/or an antihistamine may be administered orally 30 to 60 minutes prior to the start of the IV injection for subsequent participants.

The decision to implement premedication for IV injections in subsequent participants will be made by the investigator and sponsor and recorded in the study documentation.

Any premedications given will be documented as a concomitant therapy (see Section 7.8).

#### 7.4.2.2. Management of IV Administration Reactions

There is a risk of reaction with any biological agent administered intravenously; therefore, all participants should be monitored closely. Symptoms and signs that may occur as part of an IV injection reaction include, but are not limited to: fever, chills, nausea, headache, bronchospasm, hypotension, angioedema, throat irritation, rash, pruritus, myalgia, and dizziness. In the event that a significant IV injection reaction occurs, the following guidance should be followed:

- Supportive care should be employed in accordance with the symptoms/signs
- If a participant's injection reaction is sufficiently severe, subsequent injections in the cohort may be administered with premedication at the discretion of the investigator following agreement with the Lilly CRP or clinical pharmacologist

